**PLEASE RETAIN A COPY FOR YOUR STUDY RECORDS**

## CLINICAL PROTOCOL SYNOPSIS

|  |   |
|--|---|
| Objective(s):                     | 
Primary: To prospectively evaluate the intra-operative performance of the powered circular stapler used in left colectomy procedures in a post-market setting.
 
Secondary: To assess surgeon workload, surgeon satisfaction, and proactive surveillance of safety of the powered circular stapler used in left colectomy procedures in a post-market setting.
  |
| Study Design:                     | 
Patients scheduled to undergo a left-sided colon resection, and who meet study entry criteria, may be enrolled. Investigators will perform each procedure using the ECHELON CIRCULAR™ powered stapler according to its instructions for use (IFU). ECHELON CIRCULAR™ powered staplers will be provided to all participating sites. There will be no blinding or planned interim analysis in this study.
 
Procedures may be performed open or via minimally invasive surgery (MIS) according to institutional standard-of-care (SOC). Use of a hand port and robotic assistance are permissible providing the powered circular stapler is used to create the anastomosis. Conversion from laparoscopic to open surgery is permissible under the protocol at the surgeon's discretion for the patient's safety. Follow-up care will be documented at the first SOC post-operative visit to confirm healing of the anastomosis.
 
The final scheduled study visit will occur 28 days post-procedure (routinely scheduled follow-up with surgeon). Follow-up by phone is permissible when an on-site visit is not planned or is more than six weeks post-operative.
 |
| Number of Subjects:               | 
A total of 165 eligible subjects are planned to be enrolled in up to 12 sites to ensure at least 150 subjects complete the study. No formal hypothesis is being tested in this study, thus the sample size was not statistically sized through a power calculation, but rather is considered sufficient for a descriptive summary of stapler performance issues through confidence interval estimation and evaluation of safety. The sample size of 165 subjects is consistent with the amount of information that was planned to be collected on the powered stapler in the original study design and provides acceptable precision for estimation of the rate of stapler performance issues.
   |
| Diagnosis/Criteria for Inclusion: | 
 
1. Scheduled for colectomy with left-sided anastomosis performed with a circular stapler;
 
2. Willing to give consent and comply with all study-related evaluations; and
 
3. At least 18 years of age.
 
  |

| Diagnosis/Criteria for Exclusion: | 
Preoperative
 
 
1. Enrollment in a concurrent interventional clinical study that could impact the study endpoints;
 
2. Pregnancy;
 
3. Physical or psychological condition which would impair study participation;
 
4. Emergency surgery;
 
5. ASA Class <math>\geq</math> IV;
 
6. The subject is judged unsuitable for study participation by the Investigator; or
 
7. Unable or unwilling to provide follow-up information post-procedure.
 
 
Intraoperative
 
 
1. Undergoing multiple intraoperative synchronous colon resections;
 
2. Anastomosis not distal from splenic flexure of the colon;
 
3. Anastomosis of the colon not attempted; or
 
4. Subjects with any intraoperative findings identified by the surgeon that would preclude attempting an anastomosis with a circular stapler.
 
 |              |             |          |        |                                   |      |        |                                   |      |
|--|--|--------------|-------------|----------|--------|-----------------------------------|------|--------|-----------------------------------|------|
| Test Product:                     | ECHELON CIRCULAR™ Powered Circular Stapler: 
  
 Product Code	Description	Diameter	
   
 CDH29P	ECHELON CIRCULAR™ Powered Stapler	29mm	
 
 CDH31P	ECHELON CIRCULAR™ Powered Stapler	31mm	
  
  | Product Code | Description | Diameter | CDH29P | ECHELON CIRCULAR™ Powered Stapler | 29mm | CDH31P | ECHELON CIRCULAR™ Powered Stapler | 31mm |
| Product Code                             | Description  | Diameter     |             |          |        |                                   |      |        |                                   |      |
| CDH29P                                   | ECHELON CIRCULAR™ Powered Stapler  | 29mm         |             |          |        |                                   |      |        |                                   |      |
| CDH31P                                   | ECHELON CIRCULAR™ Powered Stapler  | 31mm         |             |          |        |                                   |      |        |                                   |      |
| Reference Product:                | No comparator product is being used in this study.  |              |             |          |        |                                   |      |        |                                   |      |

|   |  |
|---|--|
| 
Analysis of Effectiveness and Safety:
 | 
Analysis of Effectiveness
 
The primary endpoint is the number of subjects in whom a stapler performance issue is observed, where a stapler performance issue is defined as a failure of the powered circular stapler (study device) to perform per its IFU. This includes but is not limited to difficulty placing or removing the stapler, stapler misfire/failure of the device to fully fire, staple line defects, incomplete or thin donuts, tissue damage, positive intraoperative leak test, detached components, unformed staples, or any other device failure.
 
No formal hypothesis is being tested in this study.
 
The primary endpoint of stapler performance issues will be summarized by counts and percentages and a 95% confidence interval will be calculated.
 
Summary statistics as appropriate for continuous or categorical variables will be provided for assessments of surgical stress as measured by SURG-TLX and a surgeon satisfaction questionnaire.
 
Analysis of Safety
 
For this study, an adverse event is defined as any undesirable clinical occurrence in a subject that may be attributable to the study procedure or device used to create the colorectal anastomosis. Only AEs attributable to the device used to create the anastomosis or to the study procedure are to be recorded in the eCRF and reported to the Sponsor.
 
All adverse events reported during the study will be coded to the Medical Dictionary for Regulatory Activities (MedDRA). Adverse events will be summarized with counts and percentages by MedDRA system organ class and preferred term. Device-related AEs and procedure-related AEs will also be summarized by MedDRA system organ class and preferred term. These summaries will also be presented for all serious adverse events reported during the study. AEs will also be summarized by maximum severity by MedDRA system organ class and preferred term.
 |
| 
Interim Analysis:
                     | 
No interim analysis is planned.
   |

**PROTOCOL-SPECIFIC ACRONYMS AND ABBREVIATIONS**

| Acronyms/Abbreviation | Terms   |
|-----------------------|---|
| ACS NSQIP             | American College of Surgeons National Surgical Quality Improvement Program  |
| AE                    | Adverse Event   |
| ASA                   | American Society of Anesthesiologists Physical Status Classification System |
| CFR                   | Code of Federal Regulations   |
| CRA                   | Clinical Research Associate   |
| EC                    | Ethics Committee  |
| eCRF                  | Electronic Case Report Form   |
| EDC                   | Electronic Data Capture   |
| EES                   | Ethicon Endo-Surgery  |
| GCP                   | Good Clinical Practices   |
| HIPAA                 | Health Insurance Portability and Accountability Act of 1996                 |
| ICD                   | Informed Consent Document   |
| IFU                   | Instructions for Use  |
| IRB                   | Institutional Review Board  |
| LOS                   | Length of Stay  |
| MIS                   | Minimally-Invasive Surgery  |
| MM                    | Medical Monitor   |
| OR                    | Operating Room  |
| PI                    | Principal Investigator  |
| RCRI                  | Revised cardiac index   |
| SOC                   | Standard of Care  |
| SURG-TLX              | Surgery Task Load Index   |

## ETHICS

### **Institutional Review Board/Ethics Committee**

Participating investigators will ensure that this protocol, Informed Consent Document (ICD), ICD or protocol amendments, and if applicable, any other written information provided to the subjects that assist in the decision to participate are reviewed by an Institutional Review Board (IRB) or Ethics Committee (EC) that complies with governmental requirements. The approving IRB/EC will be responsible for the initial and continuing review and approval of this clinical investigation. Participating investigators will be required to promptly report to the IRB/EC as required by the IRB/EC's policies. Additionally, investigators will be required to refrain from making any changes in the clinical investigation plan without Sponsor and IRB/EC approval of an amended protocol, except where necessary to eliminate apparent immediate hazards to study subjects or others.

### **Applicable Regulations**

This study will be conducted in compliance with Good Clinical Practice and in accordance with the Declaration of Helsinki, as well as any other applicable local and country regulatory requirements.

### **Subject Information and Consent**

Regulations concerning the protection of subjects require that informed consent be obtained before a subject may participate in any clinical investigation.

An IRB/EC approved informed consent must be sought from each subject and must be appropriately documented in the subject's medical record prior to initiating the study. It is the Investigator's responsibility to obtain written informed consent from the subject, the Investigator may delegate this responsibility if appropriately documented.

The informed consent process involves the following: giving a subject adequate information concerning the study, providing adequate time for the subject to consider all available options, responding to the subject's questions, ensuring that the subject has comprehended this information and finally, obtaining the subject's written consent to participate in this study. All subjects in this study should be completely informed about the purpose, risks, benefits, and other pertinent details of this study. The informed consent process is careful to avoid the perception of any coercion or undue influence on, or inducement of, the subject to participate, and does not waive or appear to waive the subject's legal rights. The ICD is presented in native, non-technical language that is understandable to the subject.

Prior to a subject's participation in this study, an ICD will be signed and dated by the subject and person who conducted the consent discussion. The subject will be provided a copy of the signed ICD. The ICD and any other written materials provided to the subject to assist in the decision to participate must be revised whenever new information becomes available that may be relevant to their willingness to participate or continue participation in this study. Revision to the ICD and other written materials will receive IRB/EC approval before implementation. Each subject will be required to sign any amended ICD (as required by the IRB/EC) and will receive a copy of the signed ICD.

## ADMINISTRATIVE REQUIREMENTS

This study is sponsored by Ethicon Endo-Surgery, Inc. (EES, Cincinnati, OH, USA) and will be conducted in up to 12 surgery centers in the United States and/or European Union under a single protocol approved by each participating site's IRB/EC prior to implementation. The principal investigator at each study site is a surgeon qualified by education, experience, and training to perform the study procedure and to assume responsibility for the conduct of this study.

The Data Management and Biostatistics groups of Ethicon Endo-Surgery, Inc. will be responsible for the analysis of data from this protocol. An Electronic Data Capture (EDC) system will be utilized by study site personnel to transfer study data from source records (the first point of clinical data capture) onto common electronic case report forms (eCRFs). This system is a web-based, secure electronic software application [REDACTED]

[REDACTED] that is compliant with national and international Good Clinical Practice (GCP) data protection/data privacy and electronic record/electronic signature (e.g. 21 CFR Part 11) regulatory requirements.

### Protocol Modifications

All protocol amendments must be issued by the Sponsor, signed and dated by the Investigator, and should not be implemented without prior IRB/EC approval, except where necessary to eliminate immediate hazards to the subjects or when the change(s) involves only logistical or administrative aspects of the study (e.g., change in monitor(s), change of telephone number(s)). The Investigator reports the protocol amendments to the IRB/EC as per their local requirements.

## 1.0 INTRODUCTION

Surgical staplers have been utilized in colorectal procedures since the early 20th century, with intraluminal staplers used to create the anastomosis since 1979. Successful utilization of these devices, whether in open or laparoscopic procedures, requires extensive training and experience. Even with experience, device issues such as stapler misfire, incomplete firing, low surgeon satisfaction, etc., may occur. In a retrospective study of 349 colorectal resections, 67 (19%) procedures had some type of technical error. The most frequently reported issues from the analysis were positive leak tests, difficulty placing or removing the stapler, and inadequate donuts. Surgeons may also experience psychological or physical stress during procedures due to complications, workload, or other factors. Similarly, surgeon satisfaction with anastomotic procedures may be low for a variety of reasons, including need for multiple maneuvers, incomplete anastomosis, or excessive work effort.

A powered circular stapler has been developed with improved stability, more evenly-distributed compression, and a significantly reduced force-to-fire. It is expected that these design modifications will result in fewer technical issues associated with the device. This prospective clinical study will collect any performance issues in a post-market setting for the powered circular stapler in patients scheduled to undergo colectomy with left-sided colon anastomosis.

## 2.0 OBJECTIVE

**Primary:** To prospectively evaluate the intra-operative performance of the powered circular stapler used in left colectomy procedures in a post-market setting.

**Secondary:** To assess surgeon workload, surgeon satisfaction, and proactive surveillance of safety of the powered circular stapler used in left colectomy procedures in a post-market setting.

### 2.1 PRIMARY ENDPOINT

The primary endpoint is the number of subjects in whom a stapler performance issue is observed, where a stapler performance issue is defined as a failure of the powered circular stapler (study device) to perform per its IFU. This includes but is not limited to difficulty placing or removing the stapler, stapler misfire/failure of the device to fully fire, staple line defects, incomplete or thin donuts, tissue damage, positive intraoperative leak test, detached components, unformed staples, or any other device failure.

### 2.2 SECONDARY ENDPOINTS

- Assessment of surgical stress (surgeon) associated with the procedure using the Surgery Task Load index (SURG-TLX);
- Surgeon satisfaction questionnaire; and
- Surgeon grip strength using dynamometry (includes surgeon-reported age, height, and weight)

### 2.3 ADDITIONAL MEASUREMENTS / DATA COLLECTED

- Subject demographics and baseline characteristics;
- Subject height and weight;
- Relevant medical and surgical history (including diagnosis);

- If available, ICD-9 or ICD-10 codes, and subject insurance data;
- Documentation of pre-operative bowel prep and prophylactic use of antibiotics;
- Procedure approach (open, MIS);
- Procedure details (detailed in Section 3.17);
- Device usability/articulation questions (including robotic assistance);
- Occurrence of blood transfusion and rationale within the perioperative period;
- Outcome of intraoperative leak testing;
- Occurrence of device or procedure-related intraoperative and postoperative adverse events (including post-operative anastomotic leak);
- Length of hospital stay (LOS) from admission through discharge; and
- Details of discharge (skilled nursing facility, home, other - with rationale).

## **3.0 INVESTIGATIONAL PLAN**

### **3.1 OVERALL STUDY DESIGN AND PLAN - DESCRIPTION**

Patients scheduled to undergo a left-sided colon resection, and who meet study entry criteria, may be enrolled. In an effort to minimize selection bias, patients will be consecutively screened for enrollment. All subjects who meet entry criteria will be encouraged to enroll in the study. A subject will be considered enrolled once their anastomosis has been attempted with the powered circular stapler.

Procedures may be performed open or MIS according to institutional standard-of-care (SOC). Use of a hand port and robotic assistance are permissible providing the powered circular stapler is used to create the anastomosis. Conversion from MIS to open surgery is permissible under the protocol at the surgeon's discretion for the patient's safety. Follow-up care will be documented post-operatively to confirm healing of the anastomosis.

The final scheduled study visit will occur 28 days post-procedure (routinely scheduled follow-up with surgeon). Follow-up by phone for subjects is permissible when an on-site visit is not planned or more than six weeks post-operative.

### **3.2 ENROLLMENT**

A subject will be considered enrolled once their anastomosis has been attempted with the powered circular stapler (defined as mobilization of colon). Investigators will be asked to include subjects scheduled for both open and MIS procedures. A total of 165 eligible subjects are planned to be enrolled in up to 12 sites (United States and Europe) to ensure at least 150 subjects complete the study. The planned maximum number of subjects enrolled at any site should not exceed 20% of the total number of subjects enrolled in the study. Enrollment above this threshold will require Sponsor approval.

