### **3.6 SCREENING FAILURES**

All patients signing consent who do not have an anastomosis attempted with the powered circular stapler will be recorded as screen failures. The relevant electronic Case Report Form (eCRF) pages (demographics, reason for screen failure) will be completed for all screen failure subjects and the data will therefore be included in the study database.

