#### **Surgical:**

The Investigator must withdraw a subject intraoperatively for the following reasons:

- Anastomosis not distal from splenic flexure of the colon; or
- Anastomosis of the colon not attempted.

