##### Procedure Overview

The patient is prepped and draped in the lithotomy position. Abdominal cavity access is obtained via laparotomy or laparoscopy and the peritoneal cavity is explored. The section of interest in the colorectum is identified and exposed. A thorough exploration of the abdominal cavity is performed. The colon and liver surface are examined for any lesions. Adequate exposure of the left colon and mesenteric vessels is obtained, and anatomical landmarks identified.

The inferior mesenteric artery (IMA) is identified, isolated and divided. The left ureter is identified and preserved. The presacral space is entered and the rectum mobilized as appropriate. The mesentery is divided and distal transection of the colorectum is performed with linear stapler(s). The left colon is mobilized along the white line of Toldt and the mesentery is divided as needed for adequate resection and tension-free anastomosis. The inferior mesenteric vein (IMV) is ligated and divided.

If splenic flexure mobilization is needed, the patient is placed in a reverse Trendelenburg position. The omentum is freed from the transverse and descending colon. The colon is mobilized up and around the splenic flexure the lesser sac is entered. The colonic mesentery is dissected off the retroperitoneum and extended laterally toward the splenic flexure, with care taken not to injure to the splenic vessels. The IMV is taken below the ligament of Treitz.

After colon mobilization and distal division, a site is selected for proximal transection. A purse-string suture is placed in the proximal portion of the colon, an anvil is placed and secured by tying the purse-string suture. The stapler is passed transanally and the stapler trocar is brought out through the distal colorectal stump. The stapler and anvil are coupled and the device is closed and fired. The device is withdrawn and the tissue donuts from the anastomosis are inspected. A leak test with air insufflation in to the rectum is completed. Once anastomotic integrity is confirmed, hemostasis is secured. The patient's abdomen is closed and wounds are dressed.

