### **3.10 GUIDELINES FOR DOCUMENTING STAPLER PERFORMANCE ISSUES**

As described in Section 2.1, the primary endpoint for this study is the number of subjects in whom a stapler performance issue is observed for the powered circular staplers used to create the anastomosis in left-sided colectomy procedures. Under this protocol, stapler performance issues are defined as failure of the powered circular stapler (study device) to perform per its IFU. This includes but is not limited to difficulty placing or removing the stapler, stapler misfire/failure of the device to fully fire, staple line defects, incomplete or thin donuts, tissue damage, positive intraoperative leak test, detached components, unformed staples, or any other device failure.

The following data will be captured for each occurrence of a stapler issue:

- Procedure step (preparation of device for use, device deployment, intraoperative inspection of staple line, post-operative adverse event);
- Stapler Issue;
- Action taken; and
- Whether action resolved issue (Y/N).

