## 1.2 Study Design

This was a prospective open-label, multi-center clinical study designed to evaluate the intra-operative performance of the powered circular stapler in left colectomy procedures in a post-market setting. Investigators were to perform the procedure using the device in compliance with their standard surgical approach and the ECHELON CIRCULAR™ Powered Stapler IFU.

Each site utilized consecutive screening and enrollment in an effort to generate a random and representative patient population sample. Patients satisfying the entry criteria will be consented and screened. Subjects will be considered enrolled at the time of the first attempted anastomosis using the ECHELON CIRCULAR™ Powered Stapler device during their procedure. Procedures were performed either open or via minimally invasive surgery (MIS) according to institutional standard-of-care (SOC). Use of a hand port and robotic assistance were permissible providing the powered circular stapler was used to create the anastomosis. Conversion from MIS to open surgery is permissible under the protocol at the surgeon's discretion for the patient's safety. Follow-up care was documented post-operatively to confirm healing of the anastomosis. The final scheduled study visit was to occur 28 days post-procedure (routinely scheduled follow-up with the surgeon). Follow-up by phone for subjects was allowed when an on-site visit is not planned or was more than six weeks post-operative.

A total of 165 eligible subjects were planned to be enrolled in up to 12 sites (United States and Europe) to ensure at least 150 subjects complete the study. The planned maximum number of subjects enrolled at any site was not to exceed 20% of the total number of subjects enrolled in the study.

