## 8.4 Primary and Secondary Endpoints and Associated Hypotheses

### 8.4.1 Primary Endpoint and Associated Hypotheses

No formal hypotheses are specified for this study. The study endpoints are representative of endpoints that are currently reported in the available literature for stapler performance and this will allow for qualitative comparisons with the results from this study.

The primary performance endpoint in this study is the percentage of subjects who experienced a failure of the ECHELON CIRCULAR™ Powered Stapler to perform per its IFU. This includes but is not limited to difficulty placing or removing the stapler, stapler misfire/failure of the device to fully fire, staple line defects, incomplete or thin donuts, tissue damage, positive intraoperative leak test, detached components, unformed staples, or any other device failures.

The denominator for the primary endpoint will be the total number of subjects where an anastomosis was attempted and the numerator will be the number of subjects who experienced a stapler performance issue. An exact 95% confidence interval using the Clopper-Pearson method will also be estimated.

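### Protocol 3.2 equates an attempted anastomosis with colon mobilization, in conflict with Protocol 3.1 and 3.6 and SAP 1.2, so the primary denominator has no single definition

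*Protocol*

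**What the plan says.** The documents place the attempt at different moments.

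- Protocol 3.2: "A subject will be considered enrolled once their anastomosis has been attempted with the powered circular stapler (defined as mobilization of colon".
- Protocol 3.1 has the same sentence without the parenthesis: "A subject will be considered enrolled once their anastomosis has been attempted with the powered circular stapler".
- SAP 1.2: "Subjects will be considered enrolled at the time of the first attempted anastomosis using the ECHELON CIRCULAR™ Powered Stapler device during their procedure".
- Protocol 3.9, Procedure Overview, gives the order of steps: "After colon mobilization and distal division, a site is selected for proximal transection". The purse-string suture, the anvil and the transanal passage of the stapler come after that.

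The same word then drives several rules.

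- Screen failure (Protocol 3.6): "All patients signing consent who do not have an anastomosis attempted with the powered circular stapler will be recorded as screen failures". For these patients the section names only the demographics and failure-reason pages.
- Intraoperative exclusion (Protocol 3.4) and mandatory withdrawal (Protocol 3.7, Surgical): "Anastomosis of the colon not attempted".
- Full Analysis Set: Protocol 5.6 requires enrolment and an attempt with the powered stapler. SAP 6 identifies the set from one yes/no eCRF item on whether anastomosis was attempted, and does not define the word.
- Primary endpoint (SAP 8.4.1): "The denominator for the primary endpoint will be the total number of subjects where an anastomosis was attempted".

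Protocol 3.10 records, for each stapler issue, the step at which it arose: "Procedure step (preparation of device for use, device deployment, intraoperative inspection of staple line, post-operative adverse event". Device preparation is therefore a step at which an issue can count.

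**The concern.** The primary result is one proportion, subjects with a stapler issue over subjects attempted, so the moment of attempt decides who is counted.

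**Mobilization reading (Protocol 3.2).** A subject can be mobilized and then not have the circular stapler used, for example because of an intraoperative finding. That subject is attempted under 3.2 and can sit in the denominator with no chance of an issue. Read plainly, 3.6 makes the same subject a screen failure.

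**Device reading (Protocol 3.1 and 3.6, SAP 1.2).** If the stapler fails while being prepared and the surgeon abandons the powered device, the plan does not say whether an anastomosis was attempted with it. If the answer is no, the subject becomes a screen failure, and an event that 3.10 provides for leaves both numerator and denominator.

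Either outcome lowers the reported issue rate. The shift is systematic, so the confidence interval does not reflect it.

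**Working it through.** **Inputs from the documents.** N = 165 and an expected issue rate of 15% to 20% (Protocol 5.7, SAP 7). Stated precision: a one-sided 95% margin of at most 5.1%.

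**Inputs assumed.** The documents give no count of mobilized subjects in whom the stapler was not used, nor of preparation failures followed by abandonment. The ranges used are u = 5 to 16 and k = 1 to 5.

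**Step 1: the plan's own figure.** Margin = 1.645 × √[p(1 − p)/n].
- p = 0.20, n = 165: 5.12%.
- p = 0.15, n = 165: 4.57%.

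The stated 5.1% reproduces after rounding and serves as the yardstick.

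**Step 2: are the two points really different?** In 3.9, mobilization and distal division come first. The proximal site, purse-string, anvil and passage of the stapler follow. A subject can therefore meet the 3.2 definition before any part of the circular stapler is used.

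**Step 3: mobilization reading.** With true rate r among exposed subjects and u unexposed among 165, the expected reported rate is r(165 − u)/165.

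| r | u = 5 | u = 16 |
|---|---|---|
| 20% | 0.20 × 160/165 = 19.4% | 0.20 × 149/165 = 18.1% |
| 15% | 0.15 × 160/165 = 14.5% | 0.15 × 149/165 = 13.5% |

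Each unexposed subject costs about 0.20/165 = 0.12 percentage points at r = 20%.

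**Step 4: device reading, with preparation failures recorded as screen failures.** With x issues reported in 165 and k failures left out, the rate should be (x + k)/(165 + k).

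| Reported | k = 1 | k = 5 |
|---|---|---|
| 33/165 = 20.0% | 34/166 = 20.5% | 38/170 = 22.4% |
| 25/165 = 15.2% | 26/166 = 15.7% | 30/170 = 17.6% |

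Each omitted failure costs about 0.5 percentage points.

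**Step 5: can the effects add?** Not for the same subject. Under the 3.2 definition a mobilized subject is already enrolled, so a later preparation failure is not lost. Steps 3 and 4 are alternatives.

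**Step 6: against the yardstick.** The largest shift is about 2.5 points (25/165 to 30/170), about half the stated margin.

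**The case against.** The strongest reply is that existing rules already keep unexposed subjects out. Intraoperative findings that rule out a circular-stapler anastomosis are an exclusion (Protocol 3.4). A subject with no attempt must be withdrawn (3.7). Protocol 5.6 asks for an attempt as well as enrolment, and the SAP does not repeat the mobilization definition. This stands in part: dilution needs someone to carry the 3.2 parenthesis across to the eCRF item. But withdrawal, the Full Analysis Set and the eCRF item all rest on the same word, and 3.2 is the only place that defines it. Someone who follows it can answer yes at mobilization.

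On preparation failures, a reader might infer that the plan discards them by rule and so selects on the outcome. The documents do not support that. No section says whether preparing the device is already an attempt. The 3.10 list, and the start of adverse event collection at an attempt to use the device (7.1), both fit a reading in which such a failure counts. A loss also requires that no powered stapler is then used: with a replacement powered stapler the subject stays in. Even then a trace remains in the screen-failure reason (3.6) and the product complaint (8.2). What stands is that the primary analysis does not draw on either record, and the plan leaves the classification open.

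A reader might also infer that sites did apply different definitions. Nothing in the documents shows this.

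**Conclusion.** The conflict is in the current text, and it reaches the primary endpoint. Applying the 3.2 definition can put subjects without stapler exposure in the denominator. The device-based reading leaves one class of device failure unclassified. Each can only lower the reported rate.

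The size rests on assumed counts. At a rate near 20%, the effect is a fall of 0.6 to 1.9 points for 5 to 16 unexposed subjects, or an understatement of 0.5 to 2.4 points for 1 to 5 omitted failures. These are alternatives, not a sum. They are smaller than the stated 5.1% margin, in a descriptive study with no hypothesis test. No stated figure in the plan is wrong on this point. It should be corrected because the study's main estimate needs one defined population and the correction is cheap.

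**What to change.** Delete the parenthesis in Protocol 3.2 that equates the attempt with mobilization. Use one definition in Protocol 3.1, 3.2, 3.6, 3.7 and 5.6 and in SAP 1.2, 6 and 8.4.1. A subject is attempted once either of these holds, whether or not the device is fired:

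- use of the powered stapler or its anvil has begun for that subject's anastomosis; or
- a stapler issue has occurred while the device was being prepared for that subject.

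Subjects whose stapler was opened, with no issue and no use, remain screen failures. Enrolling everyone for whom a stapler was opened would bring back some unexposed subjects.

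If enrolment is over, as the SAP's largely past-tense account suggests, check the screen-failure reasons, device-accountability logs (Protocol 3.12) and product complaints (8.2) for preparation failures. Add any found to the numerator and denominator of the primary endpoint, as a sensitivity analysis if their other data are missing. Report how many subjects recorded as attempted never had the stapler used.

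**Cost.** Wording changes in two documents and one reconciliation. A few subjects may be reclassified with incomplete secondary data, since screen failures have few eCRF pages and nothing is imputed. The reported rate may be slightly less favourable. The definition brings in some subjects because an issue occurred, so it leans slightly towards a higher rate. Reporting the number of opened but unused staplers would show how much.
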